Participants: 70 overweight and obese healthy male and female volunteers aged between 18 and 65 years with body mass index (BMI) of 25-35 kg/m².

Support of number of volunteers: Based on previous work we anticipate that a hypo-caloric diet alone will cause a weight loss of 3.0 ± 2.5 kg, whilst the addition of propionate-ester will cause a weight loss of 5.0 ± 2.5 kg. A power calculation shows that 26 volunteers will be need per group to detect a significant difference between groups ($p=0.05$, 0.80 power). 70 volunteers will be recruited to allow a 25% drop-out rate.

Visit 1: Health Screening

Participants will attend the NIHR/Wellcome Trust Imperial Clinical Research Facility at Hammersmith Hospital where their eligibility will be assessed. They will have a blood test (FBC, ALT, HbA1C, renal function, and lipids) and height and weight measurements will also be taken. They will also have an electrocardiogram (ECG) and blood pressure will be recorded. All women of childbearing age will have a pregnancy test.

Participants will be told not to start any other new diets or intensive exercise regimes during the study period as this may give us conflicting results.

Visit 2: Acclimatization visit (Week 0)

The main objective of this visit is to fully acclimatize the participants to the study before the baseline visit.

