Statistical analysis perform with IBM SPSS version 23. Graphs prepare with GraphPad Prism version 7.04. Data will be checked for normality using a Shapiro-Wilk test (defined as $P \geq 0.01$). Percentage of weight loss will be calculated using the weight at the end of the intervention divided by the baseline weight multiplied by 100. The results express as mean difference with \pm SEM. Mean of data will be compared within and between groups using a paired t-test or Wilcoxon signed-rank test where applicable. Analysis of variance will assess the impact of two different interventions (IPE and Inulin) on participant blood parameters across the 12-week supplementation period (baseline and week 12), with the supplementation group used to determine between-subjects differences. A p-value ≤ 0.05 will consider significant.

References:

- Abete, I. et al., 2008. Effects of two energy-restricted diets differing in the carbohydrate/protein ratio on weight loss and oxidative changes of obese men. *International journal of food sciences and nutrition*, 60 Suppl 3(783016891), pp.1–13. Available at: <http://www.ncbi.nlm.nih.gov/pubmed/18654910>.
- Bouché, C. et al., 2002. Five-week, low-glycemic index diet decreases total fat mass and improves plasma lipid profile in moderately overweight nondiabetic men. *Diabetes Care*, 25(5), pp.822–828.
- Brown, A.J. et al., 2003. The orphan G protein-coupled receptors GPR41 and GPR43 are activated by propionate and other short chain carboxylic acids. *Journal of Biological Chemistry*, 278(13), pp.11312–11319.
- Chambers, E.S. et al., 2015. A novel dietary strategy to increase colonic propionate production in humans and improve appetite regulation and bodyweight management. *Nutrition Bulletin*, 40(3), pp.227–230. Available at: <http://doi.wiley.com/10.1111/nbu.12157>.
- Chambers, E.S. et al., 2014. Effects of targeted delivery of propionate to the human colon on appetite regulation, body weight maintenance and adiposity in overweight adults. *Gut*, 64(11), pp.1744–1754. Available at: <http://www.ncbi.nlm.nih.gov/pubmed/25500202>.
- Cleave, T.L., 1974. The Saccharine Disease - Chapter 5. In Bristol. Available at: http://journeytoforever.org/farm_library/Cleave/cleave_ch5.html [Accessed February 28, 2016].
- Cordain, L. et al., 2005. Origins and evolution of the Western diet : health implications for the. *The American Journal of Clinical Nutrition*, 81, pp.341–354.

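### The formula given for percentage weight loss returns the percentage of baseline weight retained, so its values, group means and the direction of the group contrast are wrong as written

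*Combined protocol and SAP*

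**What the plan says.** The Statistical Plan gives one formula for a weight outcome: "Percentage of weight loss will be calculated using the weight at the end of the intervention divided by the baseline weight multiplied by 100". The sentence contains neither a subtraction from 100 nor a change in weight in the numerator, and nothing elsewhere in the document replaces or qualifies it.

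The same section says "The results express as mean difference with" SEM, without stating the order of subtraction or the variables covered. It then adds: "Mean of data will be compared within and between groups using a paired t-test or Wilcoxon signed-rank test where applicable". It does not say whether the weight comparisons use the percentage or kilograms.

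The paragraph supporting the number of volunteers treats weight loss as a positive quantity that is larger with the active supplement. For the control arm it anticipates that "a hypo-caloric diet alone will cause a weight loss of 3.0 ± 2.5 kg". For the active arm the corresponding statement reads "whilst the addition of propionate-ester will cause a weight loss of 5.0 ± 2.5 kg".

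**The concern.** A variable labelled as loss should be zero when nothing is lost and should rise as more is lost. This one is 100 when nothing is lost and falls as more is lost. It therefore runs opposite to the convention in the sample-size paragraph, where the ester arm has the larger loss.

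Weight loss is in the trial's title and is the outcome behind the sample size. If the formula were applied literally, every individual value and group mean reported under this label would be wrong, and the arm doing better would appear to do worse. Because the plan does not fix a direction for its mean difference, nothing in the text would alert a reader to the reversed sign. A within-group analysis of the percentage, if one were run against zero, would also be meaningless.

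**Working it through.** **Inputs.** From the sample-size paragraph: anticipated loss 5.0 kg (ester) and 3.0 kg (diet alone, taken as the inulin arm), SD 2.5 kg in each (reading ± as SD), 26 per group, power 0.80, significance level 0.05. Baseline weight is not given; 75, 90 and 105 kg are assumed for illustration.

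**The plan's own figure.** For a difference of 2.0 kg with SD 2.5 kg, a two-sided two-sample t-test at 0.05 with 80% power needs 25.5 per group, rounded up to 26 (power 0.807 at 26). Allowing for 25% drop-out, 52 / 0.75 = 69.3, rounded up to 70. Both planned numbers are reproduced. They rest on kilograms and do not use the percentage formula.

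**Identity.** Let B be baseline weight and E end weight.

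- As written: R = E / B × 100
- True percentage loss: L = (B − E) / B × 100 = 100 − R

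So R = 100 − L for every participant, whatever B is. For either order of subtraction, the difference between group means of R is minus the difference between group means of L.

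**Values at the anticipated losses (%; contrast is ester minus inulin, in points).**

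| Assumed baseline | Ester, written | Inulin, written | Contrast, written | Ester, true | Inulin, true | Contrast, true |
|---|---|---|---|---|---|---|
| 75 kg | 70/75 = 93.33 | 72/75 = 96.00 | −2.67 | 6.67 | 4.00 | +2.67 |
| 90 kg | 85/90 = 94.44 | 87/90 = 96.67 | −2.22 | 5.56 | 3.33 | +2.22 |
| 105 kg | 100/105 = 95.24 | 102/105 = 97.14 | −1.90 | 4.76 | 2.86 | +1.90 |

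A participant of 90 kg who gains 2 kg scores 92/90 = 102.2% as written; the true value is −2.2%.

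**What does not change.** Subtracting a variable from 100 leaves its SD and SEM alone and only flips the sign of the between-group t statistic. In one simulated data set (26 per arm, baseline mean 90 kg and SD 12 kg assumed, losses as planned), the two-sample t was −3.766 as written and +3.766 for true loss. The p-value was 0.00044 and the ester-arm SEM 0.481 under both formulas. The rank-test p-value was also identical. A Shapiro-Wilk check is unaffected for the same reason.

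**Within-group test, only if the percentage is tested against zero.** Take n = 26, SD 2.5 kg and baseline fixed at 90 kg. The SEM is (2.5 / 90 × 100) / √26 = 0.545 points.

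- No mean loss: t = 100 / 0.545 = 183.6 as written; true t = 0.
- Ester: 94.44 / 0.545 = 173.4 as written; 5.56 / 0.545 = 10.2 true.
- Inulin: 96.67 / 0.545 = 177.4 as written; 3.33 / 0.545 = 6.1 true.

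The smaller loss gets the larger t. Because every written value is positive, a signed-rank test would always return its minimum exact two-sided p-value, 2 × 0.5^26 = 3.0 × 10⁻⁸.

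**The case against.** The strongest reply is that this is a wording slip with little practical effect. The Statistical Plan is loosely phrased throughout, and its sentence could be read as naming the ingredients of the calculation instead of the calculation itself. Figures near 95% labelled as loss would look wrong on the first output and are recovered by subtracting from 100. The two-sided between-group inference is untouched, the sample size rests on kilograms, and percentage loss is not named as the primary outcome. All of that stands, and it limits how serious the point is. It does not make the formula right: the literal reading is the natural one, and an analyst who quietly corrects it departs from the written plan.

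A second reply is that the test against zero is not described. The plan names paired tests, and the natural pair within a group is baseline and end weight in kilograms, which the error does not touch. This also stands. The large t values above show what a conditional analysis would produce; they are not a consequence of the plan as it must be read.

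A third is that the reported mean difference may not refer to this percentage at all. That is possible, since the plan does not say. The reversal is therefore claimed only for contrasts on this variable, where it occurs in either order of subtraction.

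**Conclusion.** The concern holds. The variable called percentage of weight loss is defined as percentage of baseline weight retained. Individual values and group means under that label are wrong, and any group contrast on it has the wrong sign. At an assumed 90 kg the ester-minus-inulin contrast is −2.2 points where the true figure is +2.2; over 75 to 105 kg it is −2.7 to −1.9 where the true figure is +2.7 to +1.9. Only these magnitudes depend on the assumed weight; the reversal does not.

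The design and the two-sided between-group inference are not damaged. The error should be corrected because it sits in the only formula the plan gives for a weight outcome, and what it distorts are the values and direction that readers would take from the results.

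**What to change.** Replace the sentence in the Statistical Plan with: Percentage weight loss = (baseline weight − end-of-intervention weight) / baseline weight × 100, with positive values meaning loss.

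The cost is one sentence of wording. The formula uses the same two weights the present sentence names, and the sample size does not change.

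Separately, and not needed for this correction, the sponsor should confirm which visit supplies the baseline weight. At screening the protocol states that "height and weight measurements will also be taken", and weight is named again at weeks 4 and 8. The Visit 2 section says "The main objective of this visit is to fully acclimatize the participants to the study before the baseline visit", which points to Study visit 1 as baseline, but weight is not explicitly listed there or at week 12.

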The same measurements collected during the acclimatization visit will be repeated. The only difference would be in collecting 10 ml of postprandial blood, instead of flushing saline, at each time point of 15, 30, 60, 90, 120, 180, and 240 min to measure hormones and metabolites. These will include glucose, insulin, gastrointestinal and appetite hormones (GLP-1, pro-glucagon-derived peptide, PYY, PP, Ghrelin, Cholecystokinin), and short chain fatty acids level

Participants will be randomised to take 10 g of Propionate ester or Inulin (control) dietary supplement once a day for 84 days (12 weeks). Supplements will be given to participants in ready-to-use sachets and instructed to mix the contents into their -500 kcal/day individual diet. An independent researcher (i.e. not linked to the study) will be given the task of randomisation, which will be by sealed envelopes.

Urine will be collected throughout the study visit to measure propionate and urea concentrations. Subjects will empty their bladder before the test breakfast and collect all urine thereafter for a period of 240 min. Subjects will be provided with an appropriate measurement container to collect urine and will be asked to note the total volume following each collection.

Subjects will be asked to collect a stool sample to assess propionate levels. Subjects will collect a sample of the first stool they pass after 10:00 pm on the study day. Participants will be provided with detailed instructions of how to do this and will be given appropriate containers.

Visits 4 and 5: Study visits 2, 3 (Week 4 and week 8):

Will involve short visits to monitor weight and dietary compliance to the diet, through collecting 7-days food intake diary and taking anthropometry measurements.

Visit 6: Study visit 4 (Week 12):

At the end of 84 day supplementation period, participants will attend the NIHR/Wellcome Trust Imperial Clinical Research Facility at Hammersmith Hospital to and all measurements collected during Study Visit 1 will be repeated.

PARTICIPANT ENTRY**INCLUSION CRITERIA**

- Healthy overweight and obese volunteers (body mass index (BMI) of 25-35 kg/m²)
- Age between 18-65 years (inclusive)
- Having blood results for the following tests in the ranges of:
 - HbA1C 20-41 mmol/mol haemoglobin
 - ALT 0-40 IU/L
 - FBC :

| TEST | MALE | FEMALE |
|---------------------------------|-------------|-------------|
| WBC (x10 ⁹ /L) | 4.2-10.6 | 4.2-11.2 |
| RBC (x10 ¹² /L) | 4.23- 5.46 | 3.73-4.96 |

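### Weight loss is built from two weights only, with no analysis set or missing-data method for the 25% drop-out allowed for and no analysis role for the week 4 and week 8 weights

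*Combined protocol and SAP*

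**What the plan says.** STATISTICAL PLAN defines the weight outcome from two values: "Percentage of weight loss will be calculated using the weight at the end of the intervention divided by the baseline weight multiplied by 100". Comparisons are by simple tests: "Mean of data will be compared within and between groups using a paired t-test or Wilcoxon signed-rank test where applicable". The analysis of variance in the same paragraph is limited to blood parameters at baseline and week 12.

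Support of number of volunteers asks for 26 per group and adds: "70 volunteers will be recruited to allow a 25% drop-out rate". WITHDRAWAL CRITERIA lets participants leave at any time without a reason. It does not say whether they are followed up or how their data are used.

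Interim weights are collected. Visits 4 and 5 (weeks 4 and 8) are described thus: "Will involve short visits to monitor weight and dietary compliance to the diet". The stated purpose is monitoring, and no section gives these weights a place in the analysis.

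Weight is named at screening ("height and weight measurements will also be taken") and at weeks 4 and 8. It is not itemised for Visit 2. Visit 3 refers back to Visit 2 ("The same measurements collected during the acclimatization visit will be repeated"), and Visit 6 refers back to Visit 3 ("all measurements collected during Study Visit 1 will be repeated"). Randomisation is described under Visit 3: "Participants will be randomised to take 10 g of Propionate ester or Inulin (control) dietary supplement".

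**The concern.** Weight loss is the basis of the sample size and part of the trial's stated aim. The plan expects up to a quarter of recruits to have no final weight, but names neither an analysis set nor a missing-data method. An outcome built from baseline and final weight drops those people, even when they were weighed at week 4 or week 8.

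Two things are at stake. If drop-out is random, the discarded interim weights cost some precision. If people leave because of the weight loss they have seen so far, those who remain are a selected group, and the difference between arms among them can be too small or too large. Leaving the rule open also means that it could be chosen after the data are seen.

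**Working it through.** **1. The plan's own figures.** Inputs from Support of number of volunteers: losses of 3.0 and 5.0 kg, SD 2.5 kg (reading ± as SD), alpha 0.05 (two-sided assumed), power 0.80.
- Standard error at 26 per group: 2.5 × √(2/26) = 0.693 kg. Non-centrality: 2.0/0.693 = 2.88 on 50 df, giving power 0.807. At 25 per group power is 0.791, so 26 is reproduced.
- Drop-out: 52/0.75 = 69.3, so 70 (26/0.75 = 34.7, so 35 per arm). Also reproduced.
- 70 × 0.75 = 52.5, so about 52 people would have a final weight and about 18 would not.

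The inflation is correct, but it protects power only.

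**2. Illustration of bias.** The documents give no interim means, correlations, drop-out timing or mechanism, so these are assumptions:
- mean loss at weeks 4/8/12: inulin 1.3/2.3/3.0 kg, IPE 2.2/3.8/5.0 kg; SDs 1.5/2.0/2.5 kg;
- correlations 0.8 (weeks 4, 8), 0.7 (4, 12) and 0.85 (8, 12);
- 35 per arm, 25% lost after randomisation: one third of that at random before week 4, the rest by a logistic rule after weeks 4 and 8, with less loss making drop-out more likely. Slopes are 1.0 / 1.5 per SD of the loss observed at that visit.

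Mean estimated difference over 5,000 simulated trials per scenario (Monte Carlo error about 0.01 kg, true value 2.0 kg):

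| Drop-out rule | Completers, kg | Repeated measures, kg |
|---|---|---|
| Random | 2.00 | 2.00 |
| Absolute loss, same rule in both arms | 1.84 / 1.74 | 2.00 / 2.00 |
| Loss relative to own-arm mean, both arms | 2.01 / 2.00 | no bias |
| Absolute loss, IPE arm only | about 2.3 to 2.5 | 2.00 / 2.00 |
| Next, unobserved weight | 1.79 / 1.65 | 1.93 / 1.87 |

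Under the absolute-loss rule, drop-out is about 29% (inulin) v 21% (IPE) at slope 1.0 and 30% v 19% at slope 1.5. The largest bias on observed loss is about 0.54 kg, or 0.54/0.69 = 0.8 standard errors.

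**3. A common absolute-loss rule with almost no bias.** Let retention be proportional to exp(0.05 × week 8 loss in kg), with 25% lost overall (27.8% v 22.2%). For normal data this shifts each arm's week 12 mean by 0.05 × covariance = 0.05 × 0.85 × 2.0 × 2.5 = 0.21 kg. The shift is equal in both arms and cancels, so completers give about 2.0 kg. Unequal drop-out alone does not establish bias.

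**4. If part of the 25% is lost before randomisation.** The allowance is on people recruited, so the share lost later is unknown. With half lost before: 70 × 0.125 = 8.75 leave, 61.25 are randomised (about 31 per arm), and 8.75/61.25 = 14.3% are lost afterwards. Completers then give about 1.8 to 1.9 kg (absolute loss) or 2.2 to 2.3 kg (IPE arm only).

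**5. Precision.** Under random drop-out the completers' variance is about 5 to 13% above that of repeated measures across the two settings. With strong dependence on observed loss (absolute rule, slope 1.5) the ratio is 0.94 to 1.05, so the gain is small or nil.

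**6. Departures from missing-at-random.** With 25% lost, each 1 kg less loss assumed for IPE drop-outs lowers the difference by 0.25 × 1 = 0.25 kg. With 14.3% lost it is 0.14 kg.

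**The case against.** The strongest reply is that this is a small trial with a short plan. The inflation to 70 leaves 26 measured people per group, so a completers' analysis can be inferred. The bias is hypothetical, goes either way and stays below one standard error. Most of that stands. The inference is reasonable, but the set is not stated, and the inflation does not address bias. The general sentence on comparing means could loosely cover interim weights, but it names no time point.

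Four stronger readings are tempting and should not be drawn:

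- *Drop-out that depends on observed loss always biases completers.* It does not: see the own-arm rule and the retention rule in step 3.
- *The baseline and final visits cannot be identified.* They can. Visit 2 is described as preparation ahead of the baseline visit, which makes Visit 3 the baseline. Visit 6 closes the 84-day period, and the statistical plan pairs baseline with week 12. The only gap is that weight is not itemised for Visits 2, 3 and 6.
- *The end-of-intervention weight means each person's last weight, which shrinks the effect.* Visit 6 and the statistical plan point to week 12. Under the assumed means and random drop-out, last weight gives 1.85 kg if people lost before week 4 are excluded, and 1.85 × 0.917 = 1.70 kg if they count as zero loss (8.3% lost before week 4). Neither figure comes from the documents.
- *Analysing kg changes the primary scale.* No primary outcome is named, and the power calculation is already in kg.

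**Conclusion.** The point holds as a gap in specification with a better method available from data already collected. The weight outcome uses two weights, no analysis set or missing-data method is given for the drop-out allowed for, and the week 4 and week 8 weights are unused.

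The size is modest. In the illustration, completers miss a true 2.0 kg by about −0.3 to +0.5 kg when drop-out depends on observed loss and all 25% occurs after randomisation. The error is smaller if some occurs before. Repeated measures recovers about 2.0 kg in those cases, and reduces but does not remove the bias when drop-out depends on unobserved weight. All these sizes rest on assumed interim means, correlations, timing and mechanisms.

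A reader might infer that the trial's result will be biased, or that the sample size is wrong. The documents support neither: the mechanism is unknown, and the drop-out arithmetic is right. This is a cheap improvement that should be made.

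**What to change.** Add to STATISTICAL PLAN wording such as:

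> Weight change in kg will be analysed by allocated group with a likelihood-based repeated-measures model of weeks 4, 8 and 12, in all randomised participants with any post-baseline weight. Terms: treatment, visit, treatment × visit, baseline weight and baseline × visit. The estimate is the week 12 difference. Percentage change will be reported alongside. Sensitivity analyses: participants with a week 12 weight; and a delta-adjusted analysis that includes all randomised participants, over a stated range of deltas. Numbers lost before week 4 will be reported by arm.

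Kg matches the scale of the power calculation. Multiple imputation in all randomised participants, using the interim weights, is an acceptable alternative to the main model. Add one line to the visit descriptions confirming that weight is recorded at Visit 3 and Visit 6.

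The cost is wording and slightly more analysis work, with no new visits. There are two limits. The model relies on missing-at-random given the observed weights. It also leaves out people lost before week 4, which is why the delta-adjusted analysis and the count by arm are needed.

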Administering NDCs that promote the production of propionate is an attractive way to increase the level of propionate over an extended period of time. However, due to variability of the gut microbita activity, administering high proportions ($\geq 35\text{g/d}$) of dietary fibres in human diets to increase colonic propionate does not reliably or predictably provide the same SCFA levels in colon or systemically (Cummings 1981). Oral propionate supplementation is another method, but unfortunately its short plasma half-life, poor palatability, and the fact that its main absorption happens in the small intestine limit its use as a food supplement (Frost et al. 2003).

A novel system has been developed by [name], (Scottish Universities Environmental Research Centre (SUERC)). This molecule of inulin ($\beta(2-1)$ linked polymer of fructose) carrier with an ester linked to propionate (propionate ester) was demonstrated to reliably and reproducibly increase colonic propionate while prevent the side effects of NDC (Chambers et al. 2015). Thus, propionate is only released when the carrier molecule inulin is fermented by colon microflora, which was estimated to be 180 minutes post-ingestion. (Chambers et al. 2014). Chambers et al. (2015) were able to show that 10g of Inulin-Propionate Esters (IPE) has the ability to deliver 2.4g of propionate to the colon, that is an increment of 2.5-fold of propionate production in the colon, a level that is achieved only with 60g/d via traditional dietary fibre supplementation.

The same group has also demonstrated that while the acute administration of this supplement caused increments in Plasma GLP-1 and PYY and reduced food ingestion, the long term (24 weeks) supplementation of propionate ester significantly reduced body weight gain and the development of abdominal adipose tissue (Chambers et al. 2014). Interestingly, none of the long term participants reported any side effects from the intake of propionate esters. Increasing colonic propionate is, therefore, one of the attractive strategies to manage weight and diabetes risk factors.

The current protocol aims to investigate the impact of the propionate ester in conjugation with restricted diet on appetite and weight loss.

2. Study: Effect of increased colonic propionate on weight loss during a hypo-caloric diet.

Study methodology: A randomised, control, paralleled study.

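### The only tests named for comparing IPE with inulin on weight loss are paired tests, but the two arms are independent and unmatched

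*Combined protocol and SAP*

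**What the plan says.** Section 2 describes the design as "A randomised, control, paralleled study". Under Visit 3, each participant is allocated to propionate ester or to inulin for 12 weeks. Nobody receives both, and no matching of participants across arms is described.

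Under the heading on support of the number of volunteers, the trial is sized on weight loss: "a hypo-caloric diet alone will cause a weight loss of 3.0 ± 2.5 kg", while "the addition of propionate-ester will cause a weight loss of 5.0 ± 2.5 kg". From this, "26 volunteers will be need per group to detect a significant difference between groups", with 0.80 power at p = 0.05, and 70 are recruited to allow for 25% dropout.

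The STATISTICAL PLAN section starts with a Shapiro-Wilk normality check, gives a formula for percentage weight loss, and then states: "Mean of data will be compared within and between groups using a paired t-test or Wilcoxon signed-rank test where applicable". The next sentence is the only other inferential method in the plan: "Analysis of variance will assess the impact of two different interventions (IPE and Inulin) on participant blood parameters", from baseline to week 12, with supplementation group as the between-subjects factor. No independent-samples t-test, Mann-Whitney test, ANCOVA or mixed model is named for weight, appetite scores or food intake.

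**The concern.** A paired test works on within-pair differences. Here natural pairs exist only within a person, between baseline and week 12. Between arms there are none, so an analyst following the text would have to invent them, in practice by the row order of the data file.

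This has three consequences:

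- With equal numbers of completers, the p-value changes with an arbitrary ordering.
- With unequal numbers the test cannot be run unless completers are discarded.
- The part of the sentence that does work is the within-group comparison. Both arms follow an energy-restricted diet, so both should show clear weight loss whatever the supplement does. If that comparison became the basis for conclusions, it would say nothing about propionate.

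**Working it through.** **Inputs.** From the sample-size paragraph: mean losses of 3.0 and 5.0 kg (difference 2.0), SD 2.5 kg in each arm, 26 per group, power 0.80, 25% dropout, 70 in total. Alpha is 0.05. Assumptions: a two-sided test, because sidedness is not stated; 1:1 allocation (35 per arm), because no ratio is stated; dropout independent between people; kg change as the outcome tested.

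**1. Reproduce the plan's figure.** For two independent samples of size n, the noncentrality is 2.0 / (2.5 × √(2/n)) with 2n − 2 degrees of freedom. At n = 26 this is 2.884 with 50 df.

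| n per group | Power, independent t-test |
|---|---|
| 25 | 0.791 |
| 26 | 0.807 |

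So 26 is the smallest n that reaches 0.80. A one-sided normal-approximation calculation gives 20 and does not fit. For dropout, 52 / 0.75 = 69.3, which rounds up to 70. Both stated figures are recovered. By contrast, a genuinely paired design with an assumed within-pair correlation of 0.5 would need 15 pairs, and arbitrary pairs (correlation 0) would need 27.

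**2. Arbitrary pairing with equal arms.** At 26 pairs with zero true correlation, power is 0.792 against 0.807. Simulated type I error is 4.9%. On average, little is lost.

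**3. Dependence on row order.** Pairing leaves the mean difference unchanged but alters the SD of the differences, because the arbitrary order creates a chance correlation r. With equal SDs, t(paired) = t(independent) / √(1 − r), on 25 df. Over random orderings r has mean 0 and SD 1/√25 = 0.2, so it lies mostly within ±0.39.

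For an observed difference of 1.4 kg, t(independent) = 1.4 / (2.5 × √(2/26)) = 2.019, p = 0.049.

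- r = +0.39: t = 2.019 / 0.781 = 2.59, p about 0.016.
- r = −0.39: t = 2.019 / 1.179 = 1.71, p about 0.099.

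Simulation agrees. In 10,000 orderings of one such dataset, the central 95% of p-values ran from 0.017 to 0.100, and 44% reached 0.05.

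This example lies on the significance boundary. At an observed 2.0 kg, essentially all orderings are significant (p about 0.001 to 0.022), and at 1.0 kg fewer than 1% are. Across 2,000 simulated trials at the design assumptions, re-pairing the same data in 40 random orders gave both significant and non-significant results in about 23% of trials. A single arbitrary pairing disagreed with the independent t-test in about 5%.

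**4. Unequal completers.** Completers per arm are taken as Binomial(35, 0.75).

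- Chance of equal counts: 0.110.
- Mean absolute gap: 2.87 people.
- Power averaged over this model: about 0.81 for the independent t-test, and about 0.77 for a paired test on the smaller arm's count.
- A large imbalance of 30 against 22: 0.798 independent, 0.716 for 22 forced pairs. A gap of 8 or more has probability about 0.038, so this is close to a worst case.

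**5. The within-group test.** For the control arm alone, t = 3.0 / (2.5/√26) = 6.1, p about 0.000002. The arm without propionate ester would be highly significant by itself.

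**The case against.** The strongest reply is that this is a compressed sentence from which the unpaired tests were dropped. The analysis-of-variance sentence shows that the authors know the difference between within- and between-subject comparisons, and the closing qualifier in the test sentence could be read as leaving room for judgement. That may explain how the wording arose, but it does not supply a test. The qualifier can choose only between two paired procedures, and the analysis of variance is worded for blood parameters. On this reading the analyst would still have to choose the test for weight outside the plan.

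Several qualifications do stand. False-positive risk is not inflated when arms are equal and pairing is unrelated to outcome. The 1.4 kg and 30-against-22 examples are unfavourable cases, and the average losses are modest. The plan does not name the test behind its 26 per group, so the two-sample basis is inferred from the match. Nothing in the documents says that efficacy will be judged from within-group tests, so that risk is conditional. The plan defines weight loss as a percentage while the sample size uses kg, so the kg figures here illustrate the problem and do not describe a declared primary analysis.

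**Conclusion.** The concern holds and must be fixed. As written, the plan applies paired tests to two independent, unmatched arms and gives no valid between-group method for the outcome that set the sample size. This is a stated rule that is wrong for the design, not merely missing detail.

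The harm is an arbitrary and usually unrunnable main comparison, not an excess of false positives. The arms would have equal completers only about 11% of the time. The average cost of forcing pairs is about 4 percentage points of power (0.81 to 0.77), and significance in borderline results can turn on row order. The completer and power figures rest on 1:1 allocation, independent 25% dropout, a two-sided test and the plan's own 2.0 kg difference and 2.5 kg SD. The basic incompatibility between test and design rests on none of these.

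**What to change.** Replace the test sentence in the STATISTICAL PLAN section so that it:

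- keeps the paired t-test or signed-rank test for within-group change, labelled as descriptive;
- compares weight change from baseline to week 12 between arms with an independent-samples t-test, or Mann-Whitney U if the normality check fails; ANCOVA of week-12 weight adjusted for baseline weight is preferable for efficiency, though not needed to cure the defect;
- names an unpaired between-group method for appetite scores and food intake as well;
- states that conclusions about IPE rest only on the between-group comparison.

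The cost is a short wording change. Baseline weight is already collected and no new data are needed. With the t-test, 26 per group and 70 in total stand. If the rank test were used, the equivalent requirement would be about 28 per group at an assumed relative efficiency of 0.955 (26 / 0.955 = 27.2), and up to 31 at 0.864 (26 / 0.864 = 30.1). The plan should acknowledge this slight shortfall for the fallback.
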